#### **3.4 Exploratory endpoints**

1. The time in at least moderate intense physical activity
2. Walking time
3. Intensity of moving during walking

4. Symptoms and difficulties perceived during exercise (clinical version of the PROactive tool, C-PPAC)Active)
5. Health related quality of life as measured by SGRQ (St. George's respiratory questionnaire)
6. Change from baseline to 8 weeks between the telecoaching program and the control group in average daily number of steps, QLQ-C30 and 6 MWT.

#### **Activity monitor (Dynaport movemonitor)**

The Dynaport® is the activity monitor that will be used in this study. It will be carried one week prior to visit 3 and one week prior to visit 4. It is an electronic device that is used to measure the patient's physical activity level (number of steps/day). The activity monitor provides valuable information of different aspects (i.e. different output parameters: time spent in at least moderate physical activity (MVPA), walking time, intensity of moving during walking, ...) on physical activity, directly from the wearer, in real time and in real life. This monitor will be worn during the time patients are awake, and must not be worn during bathing or water sports activities. Mean daily step count has been chosen as primary outcome.

#### **Clinical version of the PROactive questionnaire (C-PPAC)**

The PROactive questionnaire investigates relevant dimensions of physical activity and is a PRO (patient reported outcome) tool that is developed for the measurement of physical activity in the daily life of COPD patients. The tool has 2 domain scores (difficulties experienced and experiences amount of PA) and a total score. We will use the clinical version of the PROactive tool, in which the responses are intended to reflect the patients experience over the preceding 7 days. Patients will complete the web-based version of this questionnaire on visit 3 and visit 4.

#### **QLQ-C30 (Cancer quality of life questionnaire)**

The QLQ-C30 is an internationally validated 30-item questionnaire assessing cancer-specific QOL. This widely used questionnaire comprises five functional scales (physical, social, role, cognitive and emotional functioning), 3 symptom scales (fatigue, pain, nausea and vomiting), a global health status/QoL scale, and a number of single items assessing additional symptoms commonly reported by cancer patients (dyspnea, loss of appetite, insomnia, constipation and diarrhea) and perceived financial impacts of the disease. Each linear converted scale score ranges from 0 to 100. High scores for functional scales and for the global health status/QOL indicate better functioning, whilst high scores for symptom scales represent a higher level of symptom burden.

The test takes about 10 minutes. A copy of the English version is attached in Appendix 1.

#### **SGRQ (St. George's respiratory questionnaire)**

The SGRQ is a 50-item questionnaire developed to measure health status (quality of life) in patients with diseases of airway obstruction. Score are calculated for three domains: symptoms, activity and impacts (psycho-social) as well as a total score. A minimum change in score of 4 units was established as clinically relevant after patient and clinician testing. The SGRQ has been used in a range of disease groups including asthma, chronic obstructive pulmonary disease (COPD) and bronchiectasis.

The test takes about 25 minutes. A copy of the English version is attached in Appendix 1.

#### **Six minute walking test (6MWT) and Borg CR10**

All patients will undergo the Six minute walking test (6MWT). It is a reliable, valid and responsive outcome measure in patients with COPD and cancer patients. Patients will be asked to cover as much distance as possible in 6 minutes. The test will be carried out in accordance with ATS guidelines in a quiet corridor of at least 30 meters in length. Before and at the end of the test; heart rate, oxygen saturation and symptoms of dyspnea and fatigue (Borg scale CR 10) will be recorded. The result will be recorded and expressed as meters covered and as percentage of the predicted normal value. Patients will perform 2 six minute walking tests and the best of 2 tests will be retrieved.

### **3.5 Patient characterizing and safety measures**

#### Patient characterizing:

1. Baseline demographic data  
(date of birth and gender, medical/surgical history, COPD history (if applicable), smoking history, current medication, height and weight.)
2. Lung function (Post bronchodilator spirometry, body plethysmography and diffusion capacity)
3. Medical history including oncological stage, type and treatment.
4. Co-morbidities based on self-report.

#### Safety measures:

Patients are asked to report any hospitalization and major medical events during the trial period.

#### Lung function

All lung function tests will be carried out according to ATS/ERS guidelines ([Miller et al 2005](#)) and post bronchodilator values will be recorded.

[figure not shown]
### **3.6 Trial Design**

It will be a prospective non-randomised control study in which patients are evenly divided into the telecoaching group or usual care group according to owning a smartphone and their affinity with it. It is not possible to fully blind the investigator and patients. The trial will consist of 4 visits. An outpatient clinic visit (V1), a screenings visit (V2), a third visit (V3) at which the intervention will start and where the patients will be divided into the control or the intervention group and a final visit (V4) 8 weeks after starting up the intervention (V4).

Patients in both groups will receive a brochure during V3 explaining the importance of physical activity with recommendations to improve it. This brochure will be discussed together with the patients.

In the intervention group patients will receive the usual care in combination with the telecoaching intervention consisting of the following components: 1: motivational interview with the investigator during V3 discussing motivation, barriers, favourite activities and strategies to become more active; 2: a pedometer giving direct feedback on the amount of steps; 3: the coaching application linked to the step counter, which will be installed on the patient's smartphone. 4: telephone contact when a patient is non-compliant with either the use of the coaching intervention or with achieving the PA goals for 2 consecutive weeks.

### 3.7 Study diagram

### 3.8 Trial Flowchart

	Visit 1 Outpatient clinic	Visit 2	Visit 3	Visit 4
Oncological check-up (CT/labos/...) demonstrating PR after initial treatment	X			
Informed consent		X		
Baseline demographic data		X		
Medical history including oncological stage and type, comorbidities		X		
Lung function	X			
Instruction of the importance of PA (+ explanation on the intervention)			X	
PA measurement by Dynaport movemonitor (measurement for 7 consecutive days)			X	X
Clinic version of the proactive questionnaire			X	X
QLQ-C30			X	X
6MWT			X	X
SGRQ			X	X

Legend:

**X** routine clinical practice

X Additional (study protocol)

Indicate which tests are clinical routine in context of follow up after lung cancer treatment. All other tests are in context of study protocol and will be obtained by research staff.

## 4. Trial intervention

### 4.1 Investigational Medicinal product and dosing regimen

#### Telecoaching intervention:

The intervention group receives a step counter together with a coaching application installed on their smartphone. This application is a renewed version of the program used in a previous coaching trial, conducted by our research group (Demeyer 2017) and is based on the basic principles of behavioral change and contains four major domains.

#### Motivational interviewing:

A semi-structured interview is conducted to address barriers and enables to increase physical activity. Motivation and self-efficacy scores are asked to the patient.

#### Step counter:

The step counter gives direct feedback, expressed as amount of steps taken. Patient is instructed to wear this step counter every day, around the waist or wrist, as preferred.

#### The coaching application:

The coaching application, installed on the patient's smartphone, shows a daily goal (expressed as amount of steps per day) to the patient. This start goal is individual and based on the physical activity level at the beginning of the coaching intervention. This goal is weekly revised and patients themselves are able to increase the goal every week with +500 of +1000 steps per day.

Every evening, they are able to check the daily feedback platform, which gives them insights in their physical activity pattern of the day and previous weeks. Hereby they are able to evaluate their progression. At a regular basis, 'tip of the day' messages appear as a pop-up, to keep patients motivated. The last page of the application contains an action plan with activities discussed during the motivational interview in case there are difficulties to increase or maintain the physical activity levels.

### 4.2 Drug accountability

Not applicable.

### 4.3 Subject compliance

Not applicable.

#### **4.4 Concomitant medication (non-IMP)**

Not applicable.

### **5. Selection and withdrawal of subjects**

#### **5.1 Inclusion criteria**

1. Patients diagnosed with stage III or stage IV NSCLC who have a documented disease control (stable disease, partial or complete response defined by RECIST V1.1) at least 6 months after start of first line treatment. Stage III patients can only be included, if first line treatment consisted of concurrent chemoradiotherapy and a consolidation immunotherapy if indicated (if PDL1 > 1% and no potential contraindications for immunotherapy). Stage IV patients, should have received only immunotherapy (PDL1 > 50%) or a treatment of at least 4 cycles of a platinum based chemotherapy. Maintenance therapy with chemotherapy and/or immunotherapy is allowed. Administration of local radiotherapy is allowed. Patients with documented disease control can be included in the study until 2 years after starting up initial treatment.
2. > 18 years
3. Patients who are able to engage in a remote coaching program through the use of a smartphone

#### **3.1 Exclusion criteria**

1. Patients actively participating in a pulmonary rehabilitation program
2. Patients with sequential chemoradiotherapy for stadium III non-small cell lung cancer
3. The presence of orthopedic problems not allowing an increase in PA levels

#### **5.3 Selection of participants**

Patients will be screened for inclusion in the study during follow up visits in the outpatient lung cancer clinic at visit 1 (outpatient clinic).

[figure not shown]
[figure not shown]
Patients with stage III or stage IV NSCLC are included in the study if they have a documented objective partial or complete response (defined by RECIST V 1.1) around 6 months after start of first line treatment.

Stage III patients can only be included, if first line treatment consisted of concurrent chemoradiotherapy and a consolidation immunotherapy if indicated (if PDL1 > 1% and no potential contraindications for immunotherapy).

Stage IV patients, should have received only immunotherapy (PDL1 > 50%) or a treatment of at least 4 cycles of a platinum based chemotherapy. Maintenance therapy with chemotherapy or immunotherapy is allowed. The indication to start immunotherapy or chemotherapy will be discussed case by case based on a multidisciplinary discussion (Molmoc). (cfr figure 1)

**Figure 1:**

**Stage III: CRT followed by consolidation immunotherapy**

## 5.4 Expected duration of trial

Patients will be coached for 8 weeks. A screening period of 1-2 weeks before makes a trial duration of maximum 10 weeks for this pilot study. We expect to start January 2019.

# 1. Trial Procedures

## 6.1 By visit

Describe the sequence of procedures to be performed at each visit as detailed in the time/event flowchart in section 3.6.

### Visit 1 (outpatient clinic)

Patients will be screened for inclusion in the study during follow up visits in the outpatient lung cancer clinic. If oncological check-up after starting initial lung cancer treatment (with CT thorax upper abdomen, CT-brain, ...) demonstrates **documented disease control ( stable, partial or complete response defined by RECIST V1.1)** the patient is asked to join the study. If the patient wants to join the study a screening visit (V2) will be planned. **Patients with documented disease control can be included in the study until 2 years after starting up initial treatment.**

### Visit 2 (screening visit (run-in))

During visit 2 (run-in) all eligible patients who have signed the informed consent will enter the run in epoch of 1 to 2 weeks.

Patients are asked about their medical history (baseline demographic data) and their previous respiratory treatment including their oncological stage and type. Co-morbidities will also be assessed and a basic lung function will be performed.

On visit 2 patient will receive a Dynaport movemonitor to wear one week before visit 3. For patients where the run in period is more than one week, they will receive a telephone reminder to wear PROactive monitors. Patients are instructed to wear the device during waking hours. A measurement of more than 8 hours of wearing time will be defined as a 'valid day). The tri-axial accelerometer will capture steps waked per day, movement intensity and time spent in sitting, lying walking and high-intense activities.

### Visit 3 (baseline, allocation)

Patients will complete the web-based version of the clinical visit of the PROactive questionnaire. Two six-minutes walk tests will be performed and the patient will complete the quality of life questionnaires. During visit 3, the patients are divided into either control (usual care) or telecoaching group based on personal preferences and the abilities of using and having a smartphone.

All patients will be equipped with the Dynaport movemonitor one week before visit 4 and will be instructed to wear the monitor for 7 consecutive days.

#### **Visit 4 (end of the study, 8 weeks post allocation)**

Visit 4 is the end of the study. All assessments performed on visit 3 will be repeated during this study visit.

#### **6.2 Laboratory tests**

Not applicable.

#### **5.3 Other investigations**

Not applicable.

### **7 Assessment of efficacy**

The efficacy of the intervention will primary be assessed with an activity monitor worn for one week at baseline and after 8 weeks of intervention.

### **8 Assessment of Safety**

#### **8.1 Specification, timing and recording of safety parameters**

If problems occur during the trial period, patients are asked to contact the investigator to discuss the possible adverse events. If necessary, an extra visit or consultation with a physician will be scheduled.

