#### **8.2 Procedures for recording and reporting adverse events (AE)**

*8.2.1 Definitions in Law of May 7, 2004 concerning experiments on the human person*

**Adverse reaction (AR):** all untoward and unintended responses to an investigational medicinal product or to an experiment and, when an investigational product is concerned, related to any dose administered;

**Adverse event (AE):** any untoward medical occurrence in a patient or subject of the treated group during an experiment, and which does not necessarily have a causal relationship with this treatment;

**Unexpected adverse reaction (UAR):** an adverse reaction, the nature or severity of which is not consistent with the information on the experiment, and, when a clinical trial is concerned, with the applicable product information (e.g. investigator's brochure for an unauthorized investigational

product or the patient leaflet joined to the summary of product characteristics for an authorized product);

**Serious adverse event (SAE) or serious adverse reaction (SAR):** any untoward medical occurrence or effect that results in death, is life-threatening, requires hospitalisation or prolongation of existing hospitalisation, results in persistent or significant disability or incapacity, or is a congenital anomaly or birth defect, and this, when it is a clinical trial, at any dose;

**Suspected unexpected serious adverse reaction (SUSAR):** is an AR that is serious and unexpected (meaning that nature or severity of the AR is not consistent with the Investigational Medicinal Product reference safety information, which is the Investigator's Brochure) and is judged by either the investigator or the sponsor as having a reasonable suspected causal relationship with the investigational medicinal product.

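### Safety events are requested from all patients, but no visit is set to ask about them and only coached patients may get extra calls, so events may be missed and captured unevenly

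*Protocol*

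**What the plan says.** Two places in the Protocol deal with how safety information is gathered.

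- Section 8.1, whose heading promises specification, timing and recording, says: "If problems occur during the trial period, patients are asked to contact the investigator to discuss the possible adverse events". An extra visit or consultation follows if needed. No time point or form is named.
- Section 3.5, under Safety measures, says: "Patients are asked to report any hospitalization and major medical events during the trial period". This applies to all patients, but again names no visit, form or questioner.

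The schedule does not pick this up. The flowchart in Section 3.8 has rows for consent, history, lung function, the activity monitor, the walk test and each questionnaire (for example "Clinic version of the proactive questionnaire"), but none for adverse events or hospitalisation. For Visit 3, Section 6.1 lists the PROactive questionnaire, then "Two six-minutes walk tests will be performed and the patient will complete the quality of life questionnaires", then allocation. For Visit 4 it says: "All assessments performed on visit 3 will be repeated during this study visit".

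Section 3.6 gives the intervention group a further component: "telephone contact when a patient is non-compliant with either the use of the coaching intervention" or "with achieving the PA goals for 2 consecutive weeks". Usual care has no counterpart.

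**The concern.** When and how events are collected is settled by the protocol. A later analysis plan cannot recover events that nobody asked about. As written, staff can complete every listed task at V3 and V4 without asking either group whether anything happened.

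Two consequences are possible. First, under-capture. Patients are more likely to volunteer a hospital stay than a fall or a sore knee, yet such minor complaints are plausible harms of walking more. Second, uneven capture. A coached patient who becomes ill or injured may stop meeting the step goal, which triggers a call in which the event may surface. A control in the same state triggers nothing.

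The stake is the descriptive safety account of the pilot. Section 3.1 says that a larger randomised trial may follow, and its planners would read that account. The patients have stage III or IV disease and may be on maintenance therapy, so background events during the 8 weeks are plausible. The step-count analysis is not at stake.

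**Working it through.** **Passages side by side**

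| Question | Section 3.5 | Section 8.1 | Sections 3.8 and 6.1 |
|---|---|---|---|
| Who is covered | All patients | All patients | Not addressed |
| Which events | Hospitalisation and major medical events | Any problem or possible adverse event | Not addressed |
| Who starts it | Patient asked to report; asker and occasion not stated | Patient contacts the investigator | No enquiry listed |
| When | During the trial period | If problems occur | No visit |

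Two things follow directly. Collection is requested but not scheduled. The two requests also differ in scope: a fall without injury fits Section 8.1 but need not be a major event under Section 3.5.

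**Contacts after allocation.** Both groups attend V4, 8 weeks after V3. Section 6.1 (Visit 3) also has all patients equipped with the monitor one week before V4. Whether that means a contact near week 7 or a handover at V3 is unclear, but it is the same for both groups. The one contact described for a single group is the coached group's call, conditional on two weeks of non-compliance. The telephone reminder to wear the monitor during run-in comes before allocation and is not group-specific.

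**Size, on assumptions only.** The Protocol gives no event rate and no reporting probability, so it has no figure of its own to reproduce here. The only input taken from it is 16 patients per group (Section 9.1).

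*Chance of seeing no event in 16 patients.* With true risk p and captured share s, this is (1 − p·s)^16. Assume p = 0.10.

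- Full capture: 0.90^16 = 0.19
- s = 0.9: 0.91^16 = 0.22
- s = 0.5: 0.95^16 = 0.44
- s = 0.3: 0.97^16 = 0.61

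*Expected counts with equal true risk.* The expected count is 16·p·s. Assume p from 0.20 to 0.40 (3.2 to 6.4 true events per group), captured share 0.3 to 0.7 in controls and 0.5 to 0.9 in coached patients, with coached capture never below control capture.

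- Controls: from 16 × 0.20 × 0.3 = 0.96 to 16 × 0.40 × 0.7 = 4.48
- Coached: from 16 × 0.20 × 0.5 = 1.60 to 16 × 0.40 × 0.9 = 5.76
- Apparent ratio, coached to control: from 1.0 (equal capture, so the calls add nothing) to 0.9 / 0.3 = 3.0

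*One case in absolute terms.* With p = 0.20 and capture of 0.8 coached and 0.5 control, the expected counts are 16 × 0.20 × 0.8 = 2.56 and 16 × 0.20 × 0.5 = 1.60, a gap of 0.96 events. The binomial SD of the difference is √(16 × 0.16 × 0.84 + 16 × 0.10 × 0.90) = √(2.15 + 1.44) = 1.9, so the gap is about half an SD.

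**The case against.** The case against has real force on several points.

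- *Section 3.5 is a second route.* It covers every patient and does not say that the patient must make the first move. A site could satisfy it by asking at V4. This stands: one cannot say that events surface only through patient contact under Section 8.1. But nothing tells the site to ask, or when.
- *The definition in Section 8.2.1.* A reader might infer that controls are outside safety collection, because an adverse event is defined there as "any untoward medical occurrence in a patient or subject of the treated group during an experiment". The documents do not support that. The subsection reproduces statutory definitions, its serious-event definition has no group limit, Section 8.2.2 covers all serious adverse events, and Sections 3.5 and 8.1 speak of patients generally.
- *Non-serious events.* A reader might infer that falls need not be collected, because Section 8.2.2 deals with serious events. That section governs notification to the sponsor, and Section 8.1 has no seriousness threshold. What remains is the mismatch in scope with Section 3.5 and the absence of any prompt.
- *The calls.* They are conditional and not described as safety calls, and a compliant coached patient gets none. Extra capture is therefore an inference, though a reasonable one given the trigger.
- *No comparison is planned.* Sections 3.2 to 3.4 list no safety endpoint and Section 9.2 describes no between-group safety analysis. Section 9.1 uses the controls for repeatability of the activity measures and for a later power calculation. This stands and limits the consequence to descriptive reporting.
- *Magnitude.* All rates above are assumed, and a gap of about one event would not be detectable with 16 per group.

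**Conclusion.** The point holds as a weakness in data collection. Safety information is asked of all patients but is unsolicited and unscheduled, and after allocation only coached patients may receive additional calls. Events, mainly non-serious ones, may be missed, and any descriptive counts by group may differ because of ascertainment.

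It would be too strong to say that counts will be under-recorded or will not be comparable. Both groups attend V4, staff may ask there without being told to, and the calls may add nothing. The size is unknown: the ratio of 1.0 to 3.0 and the 44% against 19% chance of seeing no event depend wholly on assumed rates. The primary analysis is not affected. This is a low-cost improvement worth making, not a flaw that undermines the trial's main result.

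**What to change.** 1. Add a safety row to the flowchart in Section 3.8 at V3 (covering run-in) and V4, and name the enquiry in the Section 6.1 visit descriptions.
2. Put the same short set of questions to both groups: hospitalisation, falls, musculoskeletal complaints and other medical events, with dates.
3. Base any descriptive safety report on that enquiry. Keep the patient-initiated route in Section 8.1 alongside it.
4. Align the scope of Sections 3.5 and 8.1, so that both state the same range of events.
5. Add one study-specific sentence that events are recorded in both groups from consent to V4. Leave the statutory definitions in Section 8.2.1 as they are.

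The cost is a short amendment and a few minutes at visits that already take place. More minor events will be recorded. No additional visit or procedure is needed.
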